6.2 Study Drug Administration

Study calendar

PROCEDURES	Pre-Study Screen ^o	Cycle 1 Day 1	Cycle 1 Day 8	Cycle 1 Day 15	Day 1 of Cycle 2 onwards (+/- 5 days)	End of Treatment (+/- 5 days)
Informed Consent	Х					
Medical History	Х					
Vital Signs (including	Х	Х	Х	Х	Х	Х
temperature, pulse and blood						
pressure)						
Confidential		2	7		V8 1	1May15

Version 8 - 2014-0379

Physical Exam and	Х	Х			Х	Х
Performance Status						
Concomitant Medications	Х	х			Х	Х
CBC with differential	X*	х	X²	X ²	X ¹ , ²	Х
Blood Chemistries	X*	Х	Х	Х	Х	Х
Bone marrow aspiration and/or biopsy	X				X³	Х
IPSS score &/or WHO disease classification	X					
Pregnancy Test (females of child-bearing potential only)	Xţ					
AE and SAE assessment	Х	Х	Х	Х	Х	Х

°Screening must be performed within 4 weeks prior to study drug initiation / study start unless otherwise indicated *CBC with differential and blood chemistries (sodium, potassium, BUN, creatinine, glucose, AST and/or ALT, total bilirubin, alkaline phosphate) must be performed within 72 hours of Cycle 1 Day 1

†Within 7 days of Day 1 in females of child-bearing potential

¹ANC must be \geq 500/mm³ and platelet count must be \geq 50,000/mm³, or have recovered to baseline hematologic values ²If platelet count \leq 25,000/mm³ or ANC \leq 500/mm³ on any ixazomib dosing day, CBC should be repeated twice weekly until counts have exceeded the prespecified values (as per Section 6.3.1)

³Bone marrow aspiration and/or biopsy required for study entry, and every 3 cycles for primary outcome unless required more frequently as clinically indicated.

Ixazomib will be self-administered primarily on an outpatient basis; but may be administered as an inpatient. 3 doses of ixazomib corresponding to the three treatment days (days 1, 8 and 15) will be dispensed for the first cycle. For subsequent cycles, up to 1 month of therapy (3 doses) may be dispensed.

On day 1 (+/- 5 days) of each cycle the following procedures will be performed and

documented: physical exam including vital signs and performance status, evaluation of concomitant medications, laboratory analysis including CBC and serum chemistries, and assessment of any side effects.

Subjects will be assessed for outcome status (i.e. maintenance of CR/CRi) every 3 cycles or as clinically indicated. Adverse events, compliance and concomitant medications will be assessed continually throughout the study; specific information will be requested at each study visit.

Patient compliance will be documented using the MD Anderson (MDACC) Research Medication Diary and will be assessed at each study visit.

Destruction of unused study drug will be in accordance with the institution's drug destruction policy.

Ixazomib Administration

All protocol-specific criteria for administration of study drug must be met and documented before drug administration. Study drug will be administered or dispensed only to eligible patients under the supervision of the investigator or identified subinvestigator(s). Patients should be monitored for toxicity, as necessary, and doses of ixazomib should be modified as needed to accommodate patient tolerance to treatment; this may include symptomatic treatment, dose interruptions, and adjustments of ixazomib dose (see Section 6.3).

Capsules of ixazomib will also be referred to as study drug. Study drug will be supplied by Millennium as capsules of 2.3, 3.0 and 4.0 mg ixazomib.

The prescribed administration of ixazomib doses in this study is 4mg ixazomib on days 1, 8 and 15 in a 28 day cycle.

Patients should be instructed to swallow ixazomib capsules whole, with water, and not to break, chew, or open the capsules. Study drug should be taken on an empty stomach (no food or drink) at least 1 hour before or 2 hours after a meal. Each capsule should be swallowed separately with a sip of water. A total of approximately 8 ounces (240 mL) of water should be taken with the capsules.

Missed doses can be taken as soon as the patient remembers if the next scheduled dose is 72 hours or more away. A double dose should not be taken to make up for a missed dose. If the patient vomits after taking a dose, the patient should not repeat the dose but should resume dosing at the time of the next scheduled dose.

Ixazomib Destruction

Investigational ixazomib (expired or end of study) should be destroyed on site according to the institution's standard operating procedure. Be sure to document removal and destruction on drug accountability logs.

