3. STUDY ENDPOINTS

3.1 Primary Endpoints

The primary efficacy endpoint is relapse free survival (RFS), defined as the interval from the date of the achievement of CR/CRi to the date of first objective documentation of disease relapse or death from any cause. Subjects who are lost to follow-up without documented relapse, or are alive at last follow-up without documented relapse will be censored at the date of their last response assessment.

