4. STUDY DESIGN

4.1 Overview of Study Design

This is an open-label single arm Phase II study in subjects with AML or high-risk MDS in CR/CRi. Patients will receive single 4mg oral dose of ixazomib on days 1, 8 and 15 of each 28-day cycle. Treatment with ixazomib will be administered for 12 cycles for patients who remain in CR.

For patients with MRD positive CR/CRi at study start, treatment with ixazomib may continue for a total of 12 cycles after achievement of MRD negativity is observed.

Patients who are experiencing clinical benefit may be eligible to continue therapy after the allotted 12 cycles after discussion with the PI and the discussion documented in the patient's medical record.

Subjects will be assessed for outcome status (i.e. maintenance of CR/CRi) every 3 cycles or as clinically indicated. Adverse events, compliance and concomitant medications will be assessed continually throughout the study; specific information will be requested at each study visit.

Study cycles will be administered every 28 days ± 5 days or upon resolution of any clinically significant study drug related AE to grade 0-1, whichever occurs first.

Administration of subsequent cycles should be administered when neutrophils recover to \geq

0.5 x 10⁹/L and platelets to \geq 50 x 10⁹/L, or to baseline levels prior to the start of the last cycle of therapy.

Ixazomib will be self-administered primarily on an outpatient basis; but may be administered as an inpatient. Patient compliance will be documented using the MD Anderson (MDACC) Research Medication Diary and will be assessed at each study visit.

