6.3 Dose-Modification Guidelines

6.3.1 Recommended ixazomib Criteria for Beginning or Delaying a Subsequent Treatment Cycle & Dose Modifications for Treatment Associated Toxicity

Treatment with ixazomib will use a cycle length of 28 days. For a new cycle of treatment to begin, the patient must meet the following criteria:

- ANC must be ≥ 500/mm³ and platelet count must be ≥ 50,000/mm³, or have recovered to baseline hematologic values
- All other nonhematologic toxicity (except for alopecia) must have resolved to ≤ Grade 1 or to the patient's baseline condition

If the patient fails to meet the above-cited criteria for initiation of the next cycle of treatment, dosing should be delayed for 1 week. At the end of that time, the patient should be re-evaluated to determine whether the criteria have been met. If the patient continues to fail to meet the above-cited criteria, delay therapy and continue to re evaluate. The maximum delay before treatment should be discontinued will be 4 weeks or at the discretion of the Principal Investigator.

All decisions for dose adjustments will be made by the MD Anderson treating physician.

For dosing recommendations upon recovery, refer to Table 6-2 and Table 6-3. Dose adjustments different than those described below are acceptable after discussion with the PI, and will require documentation of the rationale for such action.

Table 6-1 MLN908 Dose Adjustments

Dose (mg)
4.0 mg
3.0 mg
2.3 mg
Discontinue

Dosage adjustments for hematologic toxicity are outlined in Table 6-2.

Criteria	Action	
Within-Cycle Dose Modifications		
 If platelet count ≤ 25 × 10⁹/L or ANC ≤ 0.50 × 10⁹/L on a ixazomib dosing day (other than Day 1) 	 ixazomib dose should be withheld. Complete blood count (CBC) with differential should be repeated twice weekly until the ANC and/or platelet counts have exceeded the prespecified values (see Section 6.3.1) on at least 2 occasions. Upon recovery, ixazomib may be reinitiated with 1 dose level reduction. 	
Dose Modifications for Subsequent Treatment Cycles		

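### The scheduled on-treatment marrow for RFS is tied to cycle count with no calendar anchor, so delays at cycle start can postpone it and the recorded date of relapses found only that way

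*Combined protocol and SAP*

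**What the plan says.** **Assessment schedule.** Footnote 3 of the study calendar in 6.2 requires a marrow "every 3 cycles for primary outcome unless required more frequently as clinically indicated". Section 4.1 says "Subjects will be assessed for outcome status (i.e. maintenance of CR/CRi) every 3 cycles or as clinically indicated", and the body text of 6.2 repeats that sentence. None of the three places gives an interval in weeks.

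**Cycle timing.** In 6.3.1, "Treatment with ixazomib will use a cycle length of 28 days". A new cycle needs adequate neutrophils and platelets, or a return to baseline, and non-haematologic toxicity at Grade 1 or below, or at baseline. Otherwise:
- "If the patient fails to meet the above-cited criteria for initiation of the next cycle of treatment, dosing should be delayed for 1 week".
- A patient who is still not ready after that week stays off dosing and is checked again.
- On the limit: "The maximum delay before treatment should be discontinued will be 4 weeks or at the discretion of the Principal Investigator".

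Section 4.1 reads differently: "Study cycles will be administered every 28 days ± 5 days or upon resolution of any clinically significant study drug related AE to grade 0-1". There the earlier of the two conditions applies.

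**Event date.** In 3.1, RFS runs to "the date of first objective documentation of disease relapse or death from any cause". The definition in 7.1.8 ends the same way.

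**Comparator.** Section 7.1.1 compares RFS with a historical median of about 11 months and does not state how those patients were assessed.

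**The concern.** Whether a patient is tested for relapse on time should not depend on whether dosing is on time. Here it can. When a cycle start slips, the third-cycle marrow slips with it, and a relapse found only at that marrow gets a later date. The slip is not random, because it follows toxicity and marrow function.

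The trial has one arm, so no control group shares the delay. Longer recorded RFS in delayed patients would feed into the posterior median, and into a futility rule that stops when the median looks worse than the historical 11 months.

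**Working it through.** **1. The plan's own precision figure.** Section 7.1.4 gives a 95% credible interval of 7.4 to 16.3 months for 25 events and a median of 11. The approximation 11 × exp(±1.96/√25) gives 7.43 to 16.28, so the figure is reproduced. It is the yardstick for any bias.

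**2. How long three cycles can take.**
- No delay: 3 × 28 = 84 days.
- The window in 4.1 read literally: 3 × 33 = 99 days.
- A 2-week delay at each cycle start: 3 × 42 = 126 days.
- A 4-week delay at each cycle start: 3 × 56 = 168 days.

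**3. Which of these can repeat.** Table 6-2 reduces the dose one level after a start delay of more than 2 weeks. Table 6-1 lists 4.0, 3.0 and 2.3 mg, then discontinuation, and 6.3.1 bars re-escalation. A patient can therefore resume after at most two such delays in the whole trial, and a third leads to discontinuation. Delays of exactly 2 weeks do not trigger that rule, so about 126 days is the longest interval that can keep recurring.

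Two limits apply to this step. Section 6.3.1 allows documented departures after discussion with the Principal Investigator. Also, Table 6-3 ties the reduction after Grade 3 non-haematologic toxicity to non-recovery within 4 weeks, whereas the Table 6-2 row, which also names non-haematologic toxicity, uses 2 weeks. I used Table 6-2 as written.

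**4. Mean lag from relapse to documentation.** Assume exponential relapse times with median 11 months, so λ = ln 2 / 11 = 0.0630 per month, and detection at the next scheduled marrow. With interval d in months (days / 30.4375), mean lag = d / (1 − exp(−λd)) − 1/λ, where 1/λ = 15.87.

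| Interval | d (months) | 1 − exp(−λd) | Mean lag (months) | Excess over 84 days |
|---|---|---|---|---|
| 84 days | 2.760 | 0.1596 | 1.42 | – |
| 99 days | 3.253 | 0.1853 | 1.68 | 0.26 |
| 126 days | 4.140 | 0.2296 | 2.16 | 0.74 |

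The documents do not say what share of relapses is found only at scheduled marrows. At 126 days the excess is 0.74 months if all are, 0.37 if half are and 0.19 if a quarter are. On the scale of an exponential median (× ln 2 = 0.693) these become 0.51, 0.26 and 0.13 months. All apply only to patients delayed 2 weeks at every cycle start.

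**5. Whole-trial effect.** Assume 30% of patients lose 28 days per three cycles, an interval of 112 days. Simulation with a true median of 11 months gives these exponential estimates of the median:

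| Relapses found between scheduled marrows (assumed) | No delay | 30% delayed | Shift (months) |
|---|---|---|---|
| 0% | 11.98 | 12.09 | 0.11 |
| 50% | 11.49 | 11.55 | 0.06 |
| 80% | 11.19 | 11.21 | 0.02 |

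The formula agrees. The excess mean lag at 112 days is 1.91 − 1.42 = 0.49 months, and 0.3 × 0.49 × 0.693 = 0.10.

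**6. Futility rule.** At a true median of 8 months, with censoring at the last assessment and the same 30% delayed, the simulated stopping probability falls from 0.385 to 0.356 if no relapse is found between marrows. It falls from 0.569 to 0.556 if half are. With 800 simulated trials the standard error of each probability is about 0.017, so these are small changes.

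**The case against.** **Stopped dosing does not always stop the assessment clock.** A reader might infer that it does. The documents do not support this: Table 6-2 withholds doses within a cycle, but nothing says that the cycle is lengthened. Only delays at cycle start clearly move the marrow. If 4.1 is taken literally, so that whichever of its two conditions is met sooner applies, even those are capped at 99 days per three cycles. This objection stands.

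**168 days is not a sustainable interval.** A reader might multiply the 4-week maximum by three and carry that interval through the trial. Step 3 shows that the dose-reduction rule in Table 6-2 does not allow it to recur without an approved departure. This also stands.

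**Patients held for low counts are watched most closely.** A reader might infer that RFS is bound to look longer in them. They are re-evaluated after a week and repeatedly thereafter. Blood counts are taken twice weekly once a dosing-day value is at or below 25,000/mm³ for platelets or 500/mm³ for neutrophils. A marrow may be done whenever clinically indicated, and one is planned, where possible, when ixazomib stops. Relapse could be found earlier in these patients, not later, and the documents do not settle the direction.

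**What the objection leaves.** No section requires a marrow during a delay or defines a trigger for an earlier one. A platelet count between 25,000 and 50,000/mm³ that is not back to baseline delays the cycle without triggering the twice-weekly counts. Non-haematologic toxicity delays a cycle and gives no hint of relapse, so nothing prompts an early marrow.

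**Conclusion.** The point holds as a minor one. The scheduled marrow for the primary endpoint follows cycle count, so delays at cycle start can postpone it and the recorded date of relapses found only there. Deaths are unaffected.

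In patients delayed 2 weeks at every cycle start, the excess mean lag is 0.19 to 0.74 months for marrow-only shares of a quarter to all. For the whole trial it is about 0.02 to 0.11 months on the median if 30% are delayed by 28 days per three cycles, against an interval of 7.4 to 16.3. These figures rest on exponential relapse times and on assumed delay frequencies and detection shares.

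A reader might infer that this could carry the trial past the 11-month benchmark. The sizes do not support that. The ordinary 84-day spacing itself adds more (1.42 × 0.693 = 0.98 months if all relapses are found at scheduled marrows). The assessment schedule behind the historical figure is not stated, so the net bias against it cannot be determined. The case for a change is that it is cheap and separates the primary-endpoint assessment from dosing.

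**What to change.** In 4.1, in the body text of 6.2 and in study-calendar footnote 3, replace the three-cycle interval with: *every 12 weeks (± 1 week) from Cycle 1 Day 1 while on treatment, regardless of dose holds or cycle delays, and as clinically indicated*. All three places must change, or the protocol will contradict itself. Keep the relapse date as the date of the first documenting assessment.

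The cycle-timing statements in 4.1 (window or resolution, whichever comes first) and 6.3.1 (delay of up to 4 weeks or at the Principal Investigator's discretion) must also be reconciled. I take no view on which should prevail.

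The cost is protocol wording. The planned spacing stays at 12 × 7 = 84 days. Some marrows will fall away from a dosing visit, and patients with long delays may have a marrow at an earlier point in their cycle count than now planned.

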6.3 Dose-Modification Guidelines

6.3.1 Recommended ixazomib Criteria for Beginning or Delaying a Subsequent Treatment Cycle & Dose Modifications for Treatment Associated Toxicity

Treatment with ixazomib will use a cycle length of 28 days. For a new cycle of treatment to begin, the patient must meet the following criteria:

- ANC must be ≥ 500/mm³ and platelet count must be ≥ 50,000/mm³, or have recovered to baseline hematologic values
- All other nonhematologic toxicity (except for alopecia) must have resolved to ≤ Grade 1 or to the patient's baseline condition

If the patient fails to meet the above-cited criteria for initiation of the next cycle of treatment, dosing should be delayed for 1 week. At the end of that time, the patient should be re-evaluated to determine whether the criteria have been met. If the patient continues to fail to meet the above-cited criteria, delay therapy and continue to re evaluate. The maximum delay before treatment should be discontinued will be 4 weeks or at the discretion of the Principal Investigator.

All decisions for dose adjustments will be made by the MD Anderson treating physician.

For dosing recommendations upon recovery, refer to Table 6-2 and Table 6-3. Dose adjustments different than those described below are acceptable after discussion with the PI, and will require documentation of the rationale for such action.

Table 6-1 MLN908 Dose Adjustments

Dose (mg)
4.0 mg
3.0 mg
2.3 mg
Discontinue

Dosage adjustments for hematologic toxicity are outlined in Table 6-2.

Criteria	Action	
Within-Cycle Dose Modifications		
 If platelet count ≤ 25 × 10⁹/L or ANC ≤ 0.50 × 10⁹/L on a ixazomib dosing day (other than Day 1) 	 ixazomib dose should be withheld. Complete blood count (CBC) with differential should be repeated twice weekly until the ANC and/or platelet counts have exceeded the prespecified values (see Section 6.3.1) on at least 2 occasions. Upon recovery, ixazomib may be reinitiated with 1 dose level reduction. 	
Dose Modifications for Subsequent Treatment Cycles		
 Delay of > 2 weeks in the start of a subsequent cycle due to lack of toxicity recovery as defined in Section 6.2ANC < 0.50 × 10⁹/L, platelet count < 50 × 10⁹/L, or other nonhematologic toxicities > Grade 1 or not to the patient's baseline condition 	 Hold ixazomib until resolution as per criteria Section 6.3. Upon recovery, reduce ixazomib 1 dose level. The maximum delay before treatment should discontinued will be 4 weeks or at the discretion of the PI. 	
Dose Modifications for Subsequent Treatment Cycles		
All hematologic toxicities	 For hematologic toxicity that occurs during a cycle but recovers in time for the start of the next cycle,: If dose was reduced within the cycle, start the next cycle at that same dose. If due to toxicity timing, ie, after Day 15 dosing thus a dose reduction was not required at that point in the cycle, reduce ixazomil by 1 dose level at the start of that cycle. Do not reduce the dose both within a cycle and at the start of the cycle for the same most severe toxicity. 	

Table 6-2ixazomib Dose Adjustments for Treatment Related Hematologic
Toxicities

Treatment modifications due to ixazomib -related AEs are outlined in Table 6-3.

Table 6-3Ixazomib Treatment Modification (Delays, Reductions, and
Discontinuations) Due to Treatment Related Adverse Events (Non-
Hematologic Toxicities)

Adverse Event (Severity)	Action on Study Drug	Further Considerations
Peripheral Neuropathy: Grade 1	• No action	Grade 1 signs and symptoms: asymptomatic; without pain or loss of function; clinical or diagnostic observations only [14]
New or worsening Grade 1 peripheral neuropathy with pain or Grade 2	 May hold study drug until resolution to Grade ≤ 1 or baseline 	Grade 2 signs and symptoms: Moderate symptoms; limiting instrumental activities of daily living (ADL) [14]
New or worsening Grade 2 peripheral neuropathy with pain or Grade 3	 Hold study drug until resolution to Grade ≤ 1 or baseline Reduce study drug to next lower dose upon recovery 	Grade 3 signs and symptoms: severe symptoms; limiting self- care ADL; assistive device indicated [14]
New or worsening Grade 4 peripheral neuropathy	Discontinue study drug	
Grade 2 Rash	• Symptomatic recommendations as per section 6.7	The investigator and project clinician may discuss considerations for dose modifications and symptom management.
Grade 3 nonhematologic toxicity judged to be related to study drug	 Hold study drug until resolution to Grade <1 or baseline 	Symptomatic recommendations noted in Section 6.7
If not recovered to < Grade 1 or baseline within 4 weeks	 Reduce study drug to next lower dose upon return to <!--= Grade 1 or baseline
 	

Table 6-3Ixazomib Treatment Modification (Delays, Reductions, and
Discontinuations) Due to Treatment Related Adverse Events (Non-
Hematologic Toxicities)

Adverse Event (Severity)	Action on Study Drug	Further Considerations
Subsequent recurrence Grade 3 that does not recover to \leq Grade 1 or baseline within 4 weeks	 Hold study drug until resolution to Grade ≤1 or baseline Reduce study drug to next lower dose 	Monitor closely, take appropriate medical precautions, and provide appropriate symptomatic care
Grade 4 nonhematologic toxicities judged to be related to study drug	Consider permanently discontinuing study drug	Exceptions are cases in which the investigator determines the patient is obtaining a clinical benefit

Once ixazomib is reduced for any toxicity, the dose may not be re-escalated.

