Symptomatic measures such as antihistamines or corticosteroids (oral or topical) have been successfully used to manage rash and have been used prophylactically in subsequent cycles. The use of a topical, IV, or oral steroid (eg, prednisone ≤ 10 mg per day or equivalent) is permitted. Management of a Grade 3 rash may require intravenous antihistamines or corticosteroids. Administration of ixazomib (and/or other causative agent if given in combination) should be modified per protocol and re-initiated at a reduced level from where rash was noted (also, per protocol).

In line with clinical practice, dermatology consult and biopsy of Grade 3 or higher rash or any SAE involving rash is recommended. Prophylactic measures should also be considered if a patient has previously developed a rash (eg, using a thick, alcohol-free emollient cream on dry areas of the body or oral or topical antihistamines). A rare risk is Stevens-Johnson Syndrome, a severe and potentially life-threatening rash with skin peeling and mouth sores, which should be managed symptomatically according to standard medical practice. Punch biopsies for histopathological analysis are encouraged at the discretion of the investigator.

Thrombocytopenia

Blood counts should be monitored regularly as outlined in the protocol with additional testing obtained according to standard clinical practice. Thrombocytopenia may be severe but has been manageable with platelet transfusions according to standard clinical practice. Ixazomib administration should be modified as noted as per dose modification recommendations in the protocol when thrombocytopenia occurs (see Table 6-2). Therapy can be reinitiated at a reduced level upon recovery of platelet counts. A rare risk is thrombotic thrombocytopenic purpura (TTP), a rare blood disorder where blood clots form in small blood vessels throughout the body characterized by thrombocytopenia, petechiae, fever, or possibly more serious signs and symptoms. TTP should be managed symptomatically according to standard medical practice.

Neutropenia

Blood counts should be monitored regularly as outlined in the protocol with additional testing obtained according to standard clinical practice. Neutropenia may be severe but has

38

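### For a related Grade 3 non-hematologic toxicity, Table 6-2, Table 6-3, section 6.3.1 and the rash text in section 6.7 conflict in pairs on the restart dose or on whether to restart, and none is named as the default.

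*Combined protocol and SAP*

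**What the plan says.** All references are to the combined protocol and SAP.

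- **Table 6-3 (section 6.3.1), general Grade 3 row.** The entry "Grade 3 nonhematologic toxicity judged to be related to study drug" carries only an instruction to hold until recovery. The next row, for a toxicity that has not returned to "Grade 1 or baseline within 4 weeks", gives the reduction: "Reduce study drug to next lower dose upon return to" Grade 1 or baseline. A later row, "Subsequent recurrence Grade 3 that does not recover to" Grade 1 or baseline in 4 weeks, again holds and reduces. None of these rows mentions stopping.
- **Table 6-2 (section 6.3.1).** The title limits it to hematologic toxicity. Its cycle-start row is triggered by "Delay of > 2 weeks in the start of a subsequent cycle due to lack of toxicity recovery", and the listed conditions include "other nonhematologic toxicities > Grade 1 or not to the patient's baseline condition". The action is a one-level reduction on recovery, with the same 4-week limit as the section text.
- **Section 6.3.1, text.** "The maximum delay before treatment should be discontinued will be 4 weeks or at the discretion of the Principal Investigator". For dosing on recovery it sends the reader to both tables without ranking them. It also accepts other adjustments if discussed with the principal investigator and documented.
- **Section 6.7, rash.** Ixazomib is to be modified as the protocol directs and "re-initiated at a reduced level from where rash was noted", again as the protocol directs. No 4-week condition is attached.
- **After Table 6-3.** A dose reduced for toxicity may not be raised again.

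**The concern.** Two treating physicians, each following a written instruction, could restart the same patient at different doses, or one could restart where the other stops. The passages also measure different things. Table 6-2 and section 6.3.1 count the delay of the next cycle. Table 6-3 counts time to recovery and does not say when its 4 weeks begin.

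Because re-escalation is barred, the difference does not wash out in later cycles. It enters delivered dose, and it may enter time to discontinuation, which section 7.1.8 uses as an estimate of treatment failure and tolerability. It also leaves study staff unable to tell which action is per protocol and which is a departure needing a documented rationale.

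**Working it through.** The plan gives no figure to reproduce, so the check applies the written rules to dated cases.

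**Inputs.** The cycle is 28 days with doses on Days 1, 8 and 15 (section 4.1), so the next cycle is due on Day 29. The dose levels are 4.0, 3.0 and 2.3 mg, then discontinue (Table 6-1). Let *t* be the onset day and *r* the recovery day.

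- Cycle delay (Table 6-2, section 6.3.1) = *r* − 29. The triggers are more than 14 days (reduce) and 28 days (limit).
- Time to recovery (Table 6-3) = *r* − *t* if the clock starts at onset, or *r* minus the day of the first withheld dose. Both are tried because the start is undefined. The trigger is more than 28 days.

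| Case | Time to recovery | Cycle delay | One source | Other source |
|---|---|---|---|---|
| 1. Onset Day 22, recovery Day 45 | 45 − 22 = 23 d (from first withheld dose, Day 29: 16 d) | 45 − 29 = 16 d | Table 6-3: hold, no reduction stated | Table 6-2: reduce one level |
| 2. Onset Day 28, recovery Day 60 | 60 − 28 = 32 d (from Day 29: 31 d) | 60 − 29 = 31 d | Table 6-3: resume one level lower | Section 6.3.1 and Table 6-2: stop, unless the principal investigator decides otherwise |
| 3. Grade 3 rash, onset Day 10, recovery Day 20 | 20 − 10 = 10 d (from Day 15: 5 d) | none | Table 6-3: hold, no reduction stated | Section 6.7: restart at a reduced level |

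Each conflict appears on either clock.

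**How far each conflict reaches.**

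1. Table 6-2 reduces when *r* − 29 > 14, so *r* ≥ 44. On the onset clock, Table 6-3 states no reduction when *r* − *t* ≤ 28. Together these need *t* ≥ 16: onset after Day 15, with a delay of 15 to 27 days (the upper end being *t* = 28, *r* = 56). On the withheld-dose clock the start is Day 29 for such patients, and the range is 15 to 28 days.
2. A delay above 28 days means *r* ≥ 58. Table 6-3's clock starts no later than Day 29, so its 4 weeks have also passed (58 − 29 = 29). The conflict arises for any onset day in the cycle.
3. The rash conflict arises for any onset day when a Grade 3 rash recovers within 4 weeks.

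**Is an unchanged dose a fair reading of Table 6-3?** The row does not say it. Two features imply it: the 4-week condition would be pointless if every Grade 3 event led to a reduction, and the Grade 3 neuropathy row of the same table does state a reduction on recovery.

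**Size for one patient.** One level down from 4.0 mg is (4.0 − 3.0)/4.0 = 25% per dose. Suppose case 1 occurs in Cycle 1 after all three doses, and the patient completes 12 cycles without other changes. Planned dose is 12 × 3 × 4.0 = 144 mg. With the reduction it is 3 × 4.0 + 11 × 3 × 3.0 = 111 mg, which is 33/144 = 23% less. For a patient already at 2.3 mg, Table 6-1 makes the next step discontinuation. Conflict 1 then becomes unchanged dose against stopping, and in conflict 2 both routes lead to stopping.

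**The case against.** The strongest reply is that the tables can be read cumulatively: reduce if either trigger is met. Section 6.3.1 does refer to both tables, and silence in Table 6-3 is not an opposing instruction. That reading would settle case 1, but no passage adopts it, and it does not settle case 2.

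The second reply is discretion. The 4-week limit yields to the principal investigator, dose decisions belong to the treating physician, and documented departures are allowed. This softens case 2 considerably, since resuming after 4 weeks can be within the rule. It does not identify which written action is the default from which one departs.

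The third concerns rash. Section 6.7 defers to the protocol, so it can be read as yielding to Table 6-3, and its mention of agents given in combination suggests generic text in a single-agent study. That is fair. Yet it still describes restart at a reduced level, and Table 6-3 states no such action for a Grade 3 rash that recovers within 4 weeks.

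A reader might infer more than the documents support:

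- **All three actions for one patient.** An unchanged dose needs at most 28 days on Table 6-3's clock, and the 4-week limit needs a delay above 28 days. These cannot both occur, because that clock starts no later than Day 29.
- **A conflict when toxicity exceeds 4 weeks but the cycle delay is under 2.** For onset Day 8 and recovery Day 40 (32 days from onset, 11-day delay), Table 6-2 is simply not triggered. If the first withheld dose was Day 15, Table 6-3 is not triggered either (40 − 15 = 25 days).
- **An effect on the toxicity stopping rule.** Section 7.1.5 counts patients with a clinically significant related event of Grade 3 or higher. These patients would generally already be counted.
- **A frequent rash conflict.** Section 1.3 gives about 50% for rash of all grades, but section 6.7 calls it typically Grade 1 to 2, and no Grade 3 rate is given.

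**Conclusion.** The point holds as three pairwise conflicts: unchanged against reduced dose (Tables 6-3 and 6-2), reduced dose against default discontinuation (Table 6-3 against section 6.3.1 and Table 6-2), and unchanged against reduced dose after Grade 3 rash (Table 6-3 and section 6.7). The first is confined to onset after Day 15 with a cycle delay of roughly 2 to 4 weeks. The second is tempered by the principal investigator's discretion.

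For an affected patient at 4.0 mg, the first or third conflict means a permanent 25% difference per dose. The second decides whether treatment continues. How many patients would be affected cannot be derived from the documents. No sample size, error rate or stopping boundary changes.

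The conclusion assumes that the general Grade 3 row of Table 6-3 implies an unchanged dose on recovery within 4 weeks, and that the Table 6-2 row means what it says about non-hematologic toxicity. The inconsistency should be corrected. This review takes no view on which clinical rule is right.

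**What to change.** Reconcile section 6.3.1, Table 6-2, Table 6-3 and the rash paragraph of section 6.7 so that each situation has one default action:

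- State whether the cycle-delay row of Table 6-2 applies to non-hematologic toxicity.
- State the restart dose explicitly in the general Grade 3 row of Table 6-3.
- Define when the 4 weeks in Table 6-3 begin, and how they relate to the 4-week limit on cycle delay.
- Give one action for Grade 3 rash in both places.
- State which passage governs if two apply, so that use of the principal investigator's discretion is recognisable as a departure from a known default.

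The sponsor chooses the clinical action in each case. The cost is a protocol wording amendment, with no change to the statistical design.
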